Abbreviations: 100DFU = 100-day follow-up; AE= adverse event; CNS = central nervous system; CR = complete response; CT = computed tomography; D/d = day; ECG = electrocardiogram; ECOG = Eastern Cooperative Oncology Group; EOT = End Of Treatment; FSH = follicle stimulating hormone; iRECIST = immunotherapy Response Evaluation Criteria in Solid Tumors; iCR = immune complete response; INR = international normalized ratio; iPR = immune partial response; IT = intratumoral; LTSFU = Long-Term Survival Follow-up; MRI = magnetic resonance imaging; N/A = not applicable; PD-L1 = programmed cell death protein ligand 1; PET = positron emission tomography; PR = partial response; PT = prothrombin time; PTFU = Post-treatment Follow-up; PTT = partial thromboplastin time; RECIST = Response Evaluation Criteria in Solid Tumors; Q3mo = every 3 months; Q3W = every 3 weeks; Q6W = every 6 weeks; SC = subcutaneous; SAE = serious adverse event; W = week; WOCBP = women of child bearing potential.

- a. End of Treatment assessments to be performed within 7 days following subject discontinuation from the last study treatment (either CMP-001 or nivolumab). Removal of a subject from CMP-001 treatment is defined as the time in which the Investigator decides to discontinue study treatment. If a subject has CMP-001 dosing withheld for more than 3 consecutive doses for any reason during the Q3W dosing period, resumption of treatment must be discussed with the Medical Monitor, otherwise, the subject will be discontinued from study treatment and will have all EOT assessments performed.
- b. The 100DFU is a safety follow-up visit that may be conducted at the study site or via phone. This visit should occur 100 days (+7) after the EOT.
- c. Post-treatment Follow-up (PTFU) will be conducted every 3 months (± 2 weeks) for all subjects who discontinue study treatment but have not met criteria for study discontinuation. These subjects should remain on study and receive disease assessments every 3 months, until discontinuation.
- d. Long-Term Survival Follow-up (LTSFU) will be conducted every 3 months (± 4 weeks) after the EOT visit or the last disease assessment date in PTFU and may occur via phone.

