**For Grade 3 or 4 symptoms** (severe reaction, Grade 3: Prolonged [eg, not rapidly responsive to symptomatic medication and/or brief interruption of infusion]; recurrence of symptoms following initial improvement; hospitalization indicated for clinical sequelae. Grade 4: Life-threatening consequences; urgent intervention indicated):

• Immediately discontinue infusion of study drug. Begin an IV infusion of normal saline and treat the subject as follows: Recommend bronchodilators, epinephrine 0.2 to 1 mg of a 1:1000 solution for SC administration or 0.1 to 0.25 mg of a 1:10,000 solution injected slowly for IV administration, and/or diphenhydramine 50 mg IV with methylprednisolone 100 mg IV (or equivalent), as needed. Subject should be monitored until the Investigator is comfortable that the symptoms will not recur. Study drug will be permanently discontinued. Investigators should

follow their institutional guidelines for the treatment of anaphylaxis. Remain at bedside and monitor subject until recovery of the symptoms.

In case of late-occurring hypersensitivity symptoms (eg, appearance of a localized or generalized pruritus within 1 week after treatment), symptomatic treatment may be given (eg, oral antihistamine or corticosteroids).

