Treatment Effect in Non-injected Target Lesions. The treatment effect in non-injected target lesions will be assessed separately from the overall effect. The confirmed ORR in non-injected target lesions based on the RECIST v1.1 Investigator measurements will be summarized for each treatment arm in the ITT Analysis Set using the same approach as that of ORR.

D. Efficacy Analysis on Subgroups of Subjects

The below subgroup analysis (not limited to) for efficacy will be explored using forest plots.

- Age $(< 65, \ge 65)$
- Sex (M, F)
- Baseline ECOG PS $(0, 1, \ge 2)$
- LDH at Enrollment (Elevated, Normal)
- BRAF mutation (Yes, No)
- Number of Lines of Prior Therapies (1, 2, >=3 [categories can be adjusted based on the data])
- Best Response to Prior Anti-PD-L1 (CR, PR, SD, PD, NE, NA, Unknown)

- Clinical Disease Stage at Enrollment (M0/M1a/M1b, M1c/M1d)
- Tumor PD-L1 Expression (TPS: <5%, >=5%)

F. Other Efficacy Related Analysis

Listings of efficacy-related data will include the following:

- All lesion assessments (target lesion, non-target lesion, new lesion)
- Response assessments
- Time to events

IX. Safety Analyses

The assessment of safety will be based on the following assessments, summarized by treatment arm using data from the Safety Analysis Set. Subjects will be analyzed according to the actual study treatment received.

A. Exposure

The number of CMP-001 and nivolumab doses received by each subject will be summarized descriptively by treatment arm for the Safety Analysis Set. The duration of treatment, dose intensities and relative dose intensity will also be summarized separately as follows with descriptive statistics in a tabular manner and a by-subject data listing.

1. Duration of Treatment (DoT)

Duration of treatment (DoT) of CMP-001 and nivolumab will be summarized in a descriptive manner, respectively. DoT will be calculated as follows:

DoT (months) = [min(last dose date + 21, discontinuation/completion date) - first dose date] / 30.4375

Or

DoT (weeks) = [min(last dose date + 21, discontinuation/completion date) - first dose date] / 7

Regeneron Pharmaceuticals Inc. / Protocol: CMP-001-011 IQVIA Biotech (Confidential) Project # SZA58924

2. Dosing Intensities

- (1) Actual dose intensity (mg/week) will be calculated as the total actual cumulative dose received divided by duration of treatment (weeks) for CMP-001 and nivolumab, respectively.

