- (2) Planned dose intensity (mg/week) will be calculated as the total planned cumulative dose to be received divided by the planned duration of treatment (weeks) based on the protocol schedule.

Planned Duration of Treatment (weeks) = number of planned treatments * 3 (weeks)

(3) Relative dose intensity (%) will be calculated based on the actual cumulative dose received relative to the planned cumulative dose throughout the duration of treatment as follows:

Relative dose intensity (%) = (actual dose intensity / planned dose intensity) * 100%

3. Dosage Modifications

The number and percentage of subjects with dose delayed, withheld, interrupted, reduced, permanently withdrawn will be tabulated with the reasons for each treatment arm, respectively.

Dosing of CMP-001 and nivolumab, including date and time of each dose, route of administration, dose administered, location of each injection, and the volume injected into each tumor at each dosing visit will be presented in a by-subject data listing per the information from the study drug administration eCRFs.

B. Adverse Events

An AE is an untoward or medical occurrence associated with the use of study drug (active or placebo drug, biologic, or device) in subjects of clinical investigation, which does not necessarily have a causal relationship with the study drug. An AE can therefore be any unfavorable and unintended symptom, sign, disease condition, or test abnormality whether or not considered related to study drug. AEs that do not meet the definition for a Serious Adverse Event (SAE) are considered non-SAEs.

AEs should be recorded upon the first occurrence and followed until resolution. A persistent AE is continuous and does not resolve between Q3W dosing visits. The AE is documented only once unless the grade becomes more severe. If the grade becomes more severe, the AE must be reported again with the new grade.

Regeneron Pharmaceuticals Inc. / Protocol: CMP-001-011 IQVIA Biotech (Confidential) Project # SZA58924

Specifically, worsening of an ongoing TEAE (i.e., an increase to higher grade) should be recorded as a new AE. Ongoing AEs with a decrease in severity/grade do not need to be captured as new AEs. Any recurrent AE should be reported as new AE each time the AE occurs.

According to Protocol section 8.1.1, disease progression, and associated hospitalizations and deaths, are not considered an AE or SAE in this study.

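### Nivolumab relative dose intensity exceeds 100%, or is undefined, when the recorded stop falls under 21 days after the last dose, because the denominator is cut at discontinuation but the planned interval is not

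*SAP*

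**What the plan says.** SAP IX.A.1 (Duration of Treatment) gives the duration in weeks as "DoT (weeks) = [min(last dose date + 21, discontinuation/completion date) - first dose date] / 7". The end date is whichever comes first: 21 days after the last dose, or the discontinuation/completion date.

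SAP IX.A.2 (Dosing Intensities) then builds three quantities.

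- Actual: "Actual dose intensity (mg/week) will be calculated as the total actual cumulative dose received divided by duration of treatment (weeks) for CMP-001 and nivolumab, respectively".
- Planned: total planned dose over planned duration, where "Planned Duration of Treatment (weeks) = number of planned treatments * 3 (weeks"). This duration is never shortened.
- Relative: "Relative dose intensity (%) = (actual dose intensity / planned dose intensity) * 100" percent. The sentence introducing this formula describes it in words as cumulative dose received compared with cumulative dose planned over the treatment period.

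The SAP does not define the discontinuation/completion date for this purpose. It sets no minimum duration and gives no rule for a duration of zero.

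The protocol leaves room for stops soon after a dose. Section 5.1.4.2 says of a Grade 3 or 4 infusion reaction: "Study drug will be permanently discontinued". Table 1, note a, says for CMP-001: "Removal of a subject from CMP-001 treatment is defined as the time in which the Investigator decides to discontinue study treatment". The same note places the end-of-treatment assessments within a week of stopping. Section 4.5 lists clinical progression, withdrawal of consent and death among the reasons for stopping, and any of these can fall between visits.

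**The concern.** The two sides of the ratio cover different periods. The last dose counts in full in the numerator of actual intensity, but the time it was meant to cover is cut off at discontinuation. On the planned side the same dose always carries its 3 weeks. A subject who received every nivolumab dose in full and on time can therefore score well above 100%, and one stopped on the day of the only dose has a zero denominator.

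Two things are at stake. First, the formula departs from the SAP's own verbal description: one dose given out of one due is 100% in words, but 300% by formula if the stop is on day 7. Second, Protocol 5.1.1 has nivolumab visits postponed rather than skipped, so delay is the main shortfall this measure can show while a subject is on treatment. The shortened denominator can cancel it.

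The problem exists for nivolumab in both arms, where 3 weeks per planned dose matches the schedule.

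**Working it through.** **Inputs.** Nivolumab 360 mg every 3 weeks (Protocol Synopsis, dosage section; 5.1.1). The duration and intensity formulas (SAP IX.A.1-2). Twenty subjects treated, with 9 randomized to Arm A and 11 to Arm B (SAP II.C). The documents state no relative dose intensity (RDI) value, so there is no figure to reproduce.

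**Planned intensity.** For m planned doses: 360m / (3m) = 120 mg/week, whatever m is.

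**Actual intensity.** Take n full doses given exactly 21 days apart, with the recorded stop k days after the last dose, 0 ≤ k < 21.

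- Duration = [21(n-1) + k] / 7 weeks.
- Actual intensity = 360n × 7 / [21(n-1) + k] mg/week.
- RDI = actual / 120 = 21n / [21(n-1) + k].

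At k = 21 or later the rule uses last dose + 21, and RDI = 21n/21n = 100%. The formula is therefore correct when the cut does not apply.

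**Results for an on-schedule subject (%):**

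| Doses n | k = 0 | k = 1 | k = 7 | k = 14 | k = 20 |
|---|---|---|---|---|---|
| 1 | undefined | 2100 | 300 | 150 | 105 |
| 2 | 200 | 190.9 | 150 | 120 | 102.4 |
| 3 | 150 | 146.5 | 128.6 | 112.5 | 101.6 |
| 10 | 111.1 | 110.5 | 107.1 | 103.4 | 100.5 |
| 35 | 102.9 | 102.8 | 101.9 | 101.0 | 100.1 |

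For n ≥ 2 the maximum is at k = 0 and equals n/(n-1), so it never exceeds 200%.

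The cell n = 3, k = 14 can arise from the imaging schedule. After doses at weeks 1, 4 and 7, the week 10 scan may be done up to 7 days early. A stop decided that day gives 63/56 = 112.5%.

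**Masked delay.** Two doses are given 35 days apart (14 days late) and treatment stops 7 days after the second.

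- SAP rule: duration = (35 + 7)/7 = 6 weeks; 720/6 = 120 mg/week; RDI = 100%.
- Denominator run to last dose + 21: (35 + 21)/7 = 8 weeks; 720/8 = 90 mg/week; RDI = 75%.

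**Effect on an arm mean (illustration only).** Assume one affected subject and every other subject at exactly 100%.

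- One dose, k = 7: (300 + 8 × 100)/9 = 122.2%, or (300 + 10 × 100)/11 = 118.2%.
- One dose, k = 14: (150 + 800)/9 = 105.6%, or (150 + 1000)/11 = 104.5%.
- Ten doses, k = 7: (107.1 + 800)/9 = 100.8%.

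In each case the median stays at 100%.

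**The case against.** The strongest reply is that this hardly matters. SAP VI calls the analyses mainly descriptive and exploratory, 20 subjects were treated, and dose intensity feeds no test, endpoint or decision. SAP IX.A also reports dose counts, duration, and delays and withdrawals with reasons, plus a by-subject dosing listing. SAP VI.L adds the median, minimum and maximum, so an extreme value would be visible and traceable. All of this stands and limits the severity.

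The frequency is also unknown. The discontinuation date is undefined in the SAP, and the dating rule in Table 1, note a, concerns CMP-001. Many toxicities in Protocol Table 2 lead first to a dose delay, so a later stop may fall more than 21 days after the last dose, where the cut does nothing. In the infusion-reaction case the dose may be only partly given, which lowers any finite value in proportion. These points stand too.

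Three stronger readings are tempting, and the documents do not support them.

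- A reader might take 300% as the ceiling. It is only the one-dose, day-7 case; in whole days, day 1 gives 2100%.
- A reader might infer that relative dose intensity is the SAP's test of equal nivolumab delivery between arms. The SAP assigns it no such role.
- A reader might infer that the rule conceals early stopping. Early stopping still shows in the dose count and the duration. What can be concealed is delay between doses.

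None of this repairs the formula, which disagrees with the sentence that introduces it.

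**Conclusion.** The formula is wrong as written, with minor consequences. For full, on-schedule nivolumab doses it overstates relative dose intensity whenever the recorded discontinuation date is under 21 days after the last dose, and it fails for a single dose stopped the same day. The overstatement is large after one dose and fades to a few percent with long treatment. It can offset a genuine delay entirely.

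The sizes assume complete 360 mg doses, whole-day dates, and a discontinuation date recorded as the day treatment was stopped. If the end-of-treatment visit date is used instead, k can grow by up to a week, but short intervals remain possible. The documents do not show whether any of the 20 subjects meets the condition. No efficacy result is touched.

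**What to change.** Keep the SAP IX.A.1 duration as the reported duration of treatment. In IX.A.2, for nivolumab actual dose intensity, replace the denominator with (last nivolumab dose date + 21 - first nivolumab dose date)/7, without the discontinuation cut. An on-schedule subject then scores 100% whenever treatment stops, delays between doses show below 100%, and the smallest possible denominator is 3 weeks, so division by zero cannot occur.

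Relying on the SAP's verbal definition alone is less clear. It gives 100% for on-schedule subjects if planned doses are those due up to the stop. In the delay example the stop falls on day 42, when a third dose would be due, so the answer is 2/2 = 100% or 2/3 = 67% depending on how that day is counted.

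The cost is one SAP line and one derived variable, with no new data. The downside is that the intensity denominator can run up to 21 days past discontinuation, so it will not always match the reported duration; a table footnote would cover that.

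The same cut applies to CMP-001. There the planned duration also allows 3 weeks per dose despite the weekly phase: seven weekly doses run to last dose + 21 give 70 mg / 9 weeks = 7.78 against 10/3 = 3.33 mg/week, or 233%, with no cut at all. That is a separate issue to reconcile and is not solved by this change.

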## Investigational Study Drug, Dosage, and Mode of Administration:

Subjects assigned to Arm A will receive CMP-001 10 mg weekly for 7 doses (W1D1 to W7D1), after which CMP-001 10 mg IT will be administered every 3 weeks (Q3W) until a reason for treatment discontinuation is reached. A prophylaxis regimen is required before each dose of CMP-001. The first dose of CMP-001 may be administered subcutaneously (SC) or by IT injection at the discretion of the Investigator; all subsequent doses are planned to be administered by IT injection. The initial 7 CMP-001 weekly dose schedule must be completed before starting the Q3W CMP-001 dosing schedule.

Subjects in Arm A and Arm B will receive nivolumab 360 mg IV over 30 minutes at W1D1 and Q3W thereafter until the subject satisfies a condition for study treatment discontinuation. Please refer to the nivolumab Investigator's Brochure.

On visits where CMP-001 and nivolumab are both administered, CMP-001 should always be administered before nivolumab.

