#### 5.1.2. CMP-001

Subjects randomized to Arm A will receive CMP-001 10 mg weekly for 7 doses (W1D1 to W7D1), after which CMP-001 will be administered by IT injection Q3W (W10D1, W13D1, etc.). The first dose of CMP-001 may be administered SC or by IT injection, at the discretion of the Investigator; all subsequent doses are planned to be administered IT. The initial 7 CMP-001 weekly dose schedule must be completed before starting the Q3W CMP-001 dosing schedule.

On visits where both CMP-001 and nivolumab are administered, CMP-001 should always be administered before nivolumab. There is no waiting period between the end of CMP-001 administration and the initiation of nivolumab infusion.

CMP-001 should be administered until a reason for treatment discontinuation is reached (Section 4.5).

See Section 5.1.3 for dose modifications for CMP-001.

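### Planned duration of 3 weeks per treatment does not fit CMP-001's seven weekly doses: subjects dosed exactly on schedule score a relative dose intensity of 233%, 122% or 111%

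*SAP*

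**What the plan says.** SAP IX.A.1 measures duration of treatment (DoT) in weeks from real dates: "min(last dose date + 21, discontinuation/completion date) - first dose date] / 7".

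SAP IX.A.2 then has three items:

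- Item (1): actual dose intensity is the total dose received "divided by duration of treatment (weeks) for CMP-001 and nivolumab, respectively".
- Item (2): planned dose intensity is the total planned dose "divided by the planned duration of treatment (weeks) based on the protocol schedule". The only formula given for that planned duration is "Planned Duration of Treatment (weeks) = number of planned treatments * 3 (weeks". CMP-001 has no formula of its own, and planned treatments are not defined.
- Item (3): relative dose intensity (RDI) is described in words as "actual cumulative dose received relative to the planned cumulative dose throughout the duration of treatment". The formula beneath it is actual intensity over planned intensity.

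On the dosing calendar, Protocol 5.1.2 says Arm A "will receive CMP-001 10 mg weekly for 7 doses (W1D1 to W7D1", and the Synopsis says that afterwards "CMP-001 10 mg IT will be administered every 3 weeks (Q3W". For both arms, the Synopsis says subjects "will receive nivolumab 360 mg IV over 30 minutes at W1D1 and Q3W thereafter".

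**The concern.** Item (2) says the planned intensity follows the protocol schedule, but its formula allows 3 weeks for every treatment. For CMP-001 that is true only from the eighth dose. The planned duration is therefore too long and the planned intensity too low. The ratio also no longer equals the one that item (3) describes in words.

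A reader of an exposure table takes 100% to mean on schedule. Here it would not mean that for CMP-001, and an under-dosed subject could score 100% or more. RDI is the table's summary of dosing against plan for the investigational drug, so it should be readable as such.

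**Working it through.** **Inputs**

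- CMP-001, 10 mg: days 0, 7, ..., 42 from first dose, then days 63, 84, ... (Protocol 5.1.2 and Table 1). Dose n with n ≥ 7 falls on day 42 + 21(n − 7): dose 22 on day 357, dose 39 on day 714.
- 22 doses is about one year of treatment: 7 weekly plus about 15 three-weekly visits (Protocol Appendix B). 39 is the last on-schedule dose within the 2-year limit.
- Nivolumab, 360 mg: every 21 days from day 0.
- E is the end of DoT in days from first dose: last dose + 21, or the stop date if earlier (SAP IX.A.1).

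The SAP states no numerical RDI, so there is no plan figure to reproduce.

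**Formula as written, treatments read as doses**

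- Actual CMP-001 intensity = 10n / (E/7).
- Planned CMP-001 intensity = 10n / 3n = 3.33 mg/week. The count cancels, so it does not matter whether planned doses are counted per subject or over 2 years.
- RDI = 3n / (E/7). For nivolumab the dose also cancels and the expression is the same.
- For n ≥ 7 on-schedule CMP-001 doses with the full 21-day tail, DoT = 6 + 3(n − 7) + 3 = 3n − 12 weeks, so RDI = n / (n − 4).

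The last column below applies item (3)'s wording: doses given over doses scheduled before E.

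| Course | E (days) | RDI, SAP formula | Given / scheduled |
|---|---|---|---|
| CMP-001, 7 on schedule | 63 | 21/9 = 233.3% | 7/7 = 100% |
| CMP-001, 22 on schedule | 378 | 66/54 = 122.2% | 22/22 = 100% |
| CMP-001, 39 on schedule | 735 | 117/105 = 111.4% | 39/39 = 100% |
| CMP-001, 39, DoT cut at 2 years | 730 | 117/104.29 = 112.2% | 39/39 = 100% |
| CMP-001, 7 on schedule, stopped day 49 | 49 | 21/7 = 300% | 7/7 = 100% |
| CMP-001, 2 on schedule, stopped day 14 | 14 | 6/2 = 300% | 2/2 = 100% |
| CMP-001, doses on days 0, 21, 42 only | 63 | 9/9 = 100% | 3/7 = 42.9% |
| CMP-001, 7 doses two weeks apart | 105 | 21/15 = 140% | 7/9 = 77.8% |
| Nivolumab, 3 on schedule | 63 | 9/9 = 100% | 3/3 = 100% |
| Nivolumab, 3, stopped day 49 | 49 | 9/7 = 128.6% | 3/3 = 100% |
| Nivolumab, 1, stopped day 7 | 7 | 3/1 = 300% | 1/1 = 100% |
| Nivolumab, 35, DoT cut at 2 years | 730 | 105/104.29 = 100.7% | 35/35 = 100% |

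**Treatments read as 3-week cycles**

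- Seven on-schedule CMP-001 doses fill 3 cycles: planned 70/9 = 7.78 mg/week. With the full tail, actual is also 70/9, so RDI is 100%. The same holds for 22 doses (18 cycles) and 39 doses (35 cycles).
- The same seven doses stopped at day 49: actual 70/7 = 10 mg/week, RDI 10/7.78 = 128.6%.
- If the plan is instead the full 2 years, 390 mg / 105 weeks = 3.71 mg/week. Seven on-schedule doses then score 7.78/3.71 = 209%, and 22 score (220/54)/3.71 = 4.07/3.71 = 110%.

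**The case against.** **Cycles, not doses.** The SAP says doses when it counts doses and treatments in the planned-duration formula, and Protocol 5.1.1 speaks of a treatment cycle. Read as cycles over the subject's own treatment period, the formula gives 100% for the three headline subjects. It is fair to say that 233%, 122% and 111% depend on the dose reading. But the SAP does not state the cycle reading, and that reading still gives 128.6% when treatment stops mid-cycle and 209% if the plan is the full 2 years. The same perfectly dosed subject could be reported at 100%, 209% or 233%.

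**Nivolumab is a separate matter.** This is largely right. The 3-week formula fits nivolumab with a full tail. The excess comes from cutting DoT at the stop date while the planned duration keeps its last 3 weeks. The documents do not say how often that will occur. The effect is real but secondary.

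**Doses are delayed, not skipped.** Protocol 5.1.1 says so, and Table 1 footnote e requires all seven weekly doses before three-weekly dosing starts. Table 8 in Protocol 8.2.4 does list withheld doses. In any case no skip is needed: doses delayed to days 0, 21 and 42, followed by stopping, score 100%. What stands is that 77.8% for two-weekly dosing counts doses due on the original calendar, including days 63 and 84. That is a convention. The 140% from the SAP formula does not depend on it.

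**Little rides on it.** Agreed. Dose counts, DoT, dose modifications with reasons and a by-subject dosing listing are all planned (SAP IX.A). They let a reader notice the problem but do not correct the ratio.

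**Conclusion.** The concern holds. Taken literally, the planned-duration formula contradicts both the protocol schedule it claims to follow and item (3)'s own description of RDI. On-schedule CMP-001 subjects score 233.3% (7 doses), 122.2% (22) or 111.4% (39; 112.2% if DoT is cut at 730 days), and real under-dosing can appear as 100% or more. These figures assume that treatments means doses and, except where a cut is stated, that DoT runs to last dose + 21 days. Earlier stopping raises the ratio for both drugs.

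Severity is minor. One descriptive exposure statistic is affected, for 9 Arm A subjects as regards CMP-001 (SAP II.C), with a truncation effect possible for nivolumab in both arms. No efficacy or adverse event result changes.

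**What to change.** Replace the planned-duration formula with item (3)'s own wording, separately for each drug:

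- RDI = cumulative dose received / cumulative dose scheduled by the protocol from first dose up to, but not including, the end of DoT. Scheduled days are 0, 7, ..., 42, then 63, 84, ... for CMP-001, and every 21 days for nivolumab.
- Planned dose intensity = that scheduled dose / DoT. DoT then cancels, so item (3)'s words and formula agree.
- State that doses due are counted on the original calendar, whether or not doses were delayed.
- Window rule: a scheduled dose whose visit window (Protocol Table 1: ±2 days for W2D1 to W7D1, ±3 days from W10) is open when DoT ends counts as due if, and only if, it was given.

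The window rule is needed in both directions. If dose 7 is given on day 44, inside its window, DoT runs to day 65 and passes day 63: RDI is 7/8 = 87.5% without the rule and 7/7 = 100% with it. If dose 8 is given early on day 60 and treatment stops on day 61, RDI is 8/7 = 114.3% without the rule and 8/8 = 100% with it.

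The cost is one SAP definition and one derivation program. Dose dates and discontinuation dates are already collected. A smaller repair, setting planned duration from the CMP-001 schedule (9, 54 and 105 weeks for 7, 22 and 39 doses), would correct the headline cases but not the early-stopping ones.
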